11. MEASUREMENT OF EFFECT

11.1 Primary Endpoint

11.1.1 *Time to improvement (2 points) in 7-point ordinal scale*

The time to improvement (2 points) will be defined as the time (days) required from the start of treatment to the improvement of clinical status (2 points) assessment from baseline based on the 7-point ordinal scale. Patients for whom there was no event will be censored from this analysis. 7-point ordinal scale will be calculated as follows: (1) death, (2) hospitalized on invasive mechanical ventilation or extracorporeal membrane oxygenation, (3) hospitalized, requiring non-invasive ventilation or high flow nasal cannula, (4) hospitalized, requiring supplemental oxygenation (5) hospitalized, not requiring supplemental oxygenation and requiring ongoing medical care (COVID-19 related or otherwise) (6) Hospitalized, not requiring supplemental oxygen – no longer requires ongoing medical care, (7) not hospitalized.

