2. STUDY OBJECTIVES

Primary Objective

- To determine the **time to improvement in the 7-point ordinal scale** in patients treated with anti-IL-8 therapy compared to standard of care/controls.
 - Measured from baseline to 2 point or greater improvement in 7-point ordinal scale.

Secondary Objectives

- To evaluate the **time to death** in patients treated with anti-IL-8 therapy compared to controls.
- To evaluate the **mortality 1 month** after start of treatment in patients treated with anti-IL-8 therapy compared to controls.
- To determine the **time to intubation** in patients treated with anti-IL-8 therapy compared to controls.
 - Measured from time of disease onset to time of intubation.
- To estimate the **time to improvement in oxygenation** in patients treated with anti-IL-8 therapy compared to controls.
 - Measured as time from start of treatment until $\geq 30\%$ decrease in oxygen requirement compared to baseline
- To measure the **proportion of patients requiring ICU admission at 1 month** in patients treated with anti-IL-8 therapy compared to controls.
 - Measured as the number of patients requiring ICU admission over their hospitalization over the number of evaluable patients.
- To assess the **safety and tolerability** defined as adverse events graded by CTCAE v5.0 in patients treated with anti-IL-8 therapy compared to controls.
- To assess the **duration of hospitalization** in patients treated with anti-IL-8 therapy compared to controls.
 - Measured as time from admission to time of discharge.
- To compare the raw 7-point ordinal scale scores at day 14 in patients treated with anti-IL-8 therapy versus controls.

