Duration of Treatment: Subjects randomized to receive BMS-986253 will receive treatment for up to 4 weeks while hospitalized or intolerable toxicity or side effects. Patients who are discharged prior to 2 weeks after the first treatment, will not receive additional doses of therapy. Patients still with severe respiratory symptoms and hospitalized at 4 weeks may receive an additional treatment dose. Subjects randomized to the control arm will receive standard of care therapy as determined by their treating physician.

PK assessments and Correlative Studies: Serum will be collected at baseline and then weekly during hospitalization if feasible. For patients ready for discharge prior to day 8, a serum sample should be collected, when feasible, prior to discharge.

Duration of Follow up: Toxicity and laboratory tests will be graded using the NCI CTCAE v5.0 scoring system. Adverse events will be assessed continuously from the inpatient medical record during the study and for **100 days** after the last dose of treatment. Laboratories as outlined in **Section 11** will be collected daily during hospitalization. Post-discharge medical history and survival will be assessed monthly until 100 days following the last dose of therapy and then every 3 months for up to 1 year.

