In order to confirm eligibility status, Investigators/designees (e.g., study specific Clinical Research Coordinator/Research Nurse, etc.) must submit the following documentation to the Central Registration Office via email or fax:

- The completed/signed study specific Eligibility Checklist (signed by a Physician level Investigator)
- Copies of source documentation necessary for each item to be verified on the CPDM specific Eligibility Checklist, including but not limited to:
 - Copy of required laboratory test and procedure reports (e.g., hematology, serum chemistry, pregnancy test when applicable, MRI reports, CT/bone scans, etc.)
 - Copy of pathology and surgical reports
 - Copy of clinic note(s) or other appropriate medical records capturing the consent process information, along with providing source documentation of any other items needed for screening/eligibility that are not captured in other source document forms (e.g., positive investigator statements of unique eligibility items not captured via other direct source documentation, concomitant medication lists, etc.)
 - Protocol deviation/waiver approvals (if applicable)
- **Please note:** subject line of email or fax should include the following: “AAAS9881 Complete Subject Registration Request (PHI)”.

Upon receipt of the above mentioned documentation, participant eligibility information will be verified by a qualified Central Registration Registrar. If any questions arise during the review process, queries in the form of emails will be addressed to the applicable study team personnel for clarification prior to enrollment. All applicable finalized registration/eligibility information will then be entered into HICCC’s institutional CTMS database by the Central Registration Registrar. Upon completion, an official subject registration notification email will be sent to the PI/research team which will include eligibility/enrollment status, as well as subject ID information. Protocol therapy may not be initiated prior to receipt of this notification from the Central Registration Office.

All screen fail/ineligible subjects, as well as subject’s who withdraw consent prior to enrollment/initiation of protocol therapy must be submitted to the Central Registration office in a manner analogous to the procedures noted above. Applicable source documentation will be required within the corresponding submissions.

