7.5 Randomization and Blinding

Patients will be randomized 2:1 (anti-IL8: standard of care) in “real-time”. If the subject’s eligibility status is confirmed, the statistician will send the randomization assignment based on the pre-generated randomization scheme.

This is an open-label study.

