10. STUDY CALENDAR

Every effort should be made to keep visits, tests, and procedures on schedule. Acceptable deviations are listed below.

	Screening Evaluation ^a	During Hospitalization (daily unless indicated)	Day 29 and Follow-up (after discharge) ^f
Informed consent	X		
Medical history (including baseline ECOG)	X		X
Review of medications	X	X	X
Physical assessment ^k	X	X	
Vital signs (including SpO ₂ /FIO ₂ if on supplemental oxygen)	X	(3 times per day) ⁱ	
Height and weight	X		
Laboratory studies ^b	X	X	
Inflammatory markers ^j	X	Every 2 days	
NLR and absolute lymphocyte count	X	X	
Serum ^c	X	Every 7 days (+/- 2 days) ^c	
NEWS2 score ^d	X	X	
7-point ordinal scale ^l	X	X	
Chest imaging (optional) ^e	X	Every 7 days (+/- 2 days) ^e	
BMS-986253 dose		Every 2 weeks for 1-3 doses ^g	
Toxicity assessment		X	X ^h

a: The screening (pre-treatment) evaluation should be conducted within 1 day prior to dose of BMS-986253. If screening done on same day as treatment then treatment day 1 assessments do not need to be repeat (screening assessments will suffice)
b: Laboratories should include hemoglobin, hematocrit, white blood cell count with differential (including absolute eosinophil count), platelets, sodium, potassium, chloride, bicarbonate, urea nitrogen, creatinine, glucose, calcium, albumin, total protein, bilirubin, alanine aminotransferase (ALT), aspartate aminotransferase (AST), alkaline phosphatase. Prothrombin time (PT/INR), activated partial thromboplastin time (APTT) will be drawn at baseline and then as clinically indicated.
c: Serum samples should be collected for cytokine and PK analysis at screening, day 8, 15, 22, 29, and EOT if possible (not required). Should be collected prior to the treatment dose of day 15 and 29. For patients ready for discharge prior to day 8, a serum sample should be collected, when feasible, prior to discharge.
d: NEWS2 score is calculated considering respiratory rate, oxygen saturation, systolic blood pressure, pulse rate, level of consciousness/confusion, temperature.
e: CT chest or CXR at baseline (within 2 days of enrollment) and after 7 days (+/- 2 days) if clinically indicated.
f: Can be done by phone: at day 29 (+/- 1 day) and every 1 month (+/- 1 week) (until 100 days following last dose of treatment), then every 3 months (+/- 1 month) from registration to up to 1 year follow up.

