10.1 Screening/Pretreatment Evaluation

Before initiating any screening activities, the scope of the study should be explained to each patient. Patients should be advised of any known risks inherent in the planned procedures, any alternative treatment options, their right to withdraw from the study at any time and for any reason, and their right to privacy. After this explanation, patients should be asked to sign and date an IRB-approved informed consent form that meets the requirements of the Code of Federal Regulations (Federal Register Vol. 46, No. 17, January 27, 1981, part 50).

The pretreatment/screening visit will determine patient eligibility according to the inclusion and exclusion criteria. All subjects must undergo a number of baseline evaluations as part of this screening visit, as detailed below. All of these evaluations should be conducted within 1 day of starting the protocol. This information is also summarized in the Study Calendar (Table 1).

- informed consent
- demographic information
- medical history, including review of systems and baseline ECOG score.
- physical assessment
- vital signs: temperature, pulse, blood pressure, respiratory rate, oxygen saturation and FIO₂ and SpO₂/FIO₂
- height and weight
- current medication list, including drug allergies/adverse events
- hematological laboratories (hemoglobin, hematocrit, white blood cell count with differential [including absolute eosinophil count], platelets)
- coagulation profile (INR, aPTT)
- serum chemistry (sodium, potassium, chloride, bicarbonate, urea, creatinine, glucose, calcium, albumin, protein, bilirubin, ALT, AST, alkaline phosphatase)
- CRP, D-Dimer, LDH, sIL-6 level
- Neutrophil-to-lymphocyte ratio (NLR), absolute lymphocyte count
- NEWS2 score
- 7-point ordinal score
- CT or CXR of the chest (optional)
- Sera for biomarker and PK analysis.

After all relevant screening information is documented, registration should be finalized and appropriate documents (*i.e.*, signed informed consent, supporting source documentation for eligibility) should be faxed or emailed to CPDM Central Registration Office for review.

Information on patients who do not meet eligibility criteria to participate in this study (*i.e.*, screening failures) should also be captured.

10.2 During Hospitalization:

The following must be performed during hospitalization (if screening assessments done <1 day prior to first treatment dose, they do not need to be repeated on Day 1 of treatment).

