13 STATISTICAL CONSIDERATIONS

13.1 Study Design and Sample Size

This study is a single-center, randomized open-label phase 2 trial to evaluate the efficacy and safety of anti-IL-8 in hospitalized adults with severe or critical COVID-19. The primary endpoint is time to improvement in clinical status: the time (days) required from the start of treatment to the improvement of clinical status (2 points) assessment from baseline based on the 7-point ordinal scale. Patients for whom there was no event will be censored.

Patients will be randomized in a 2:1 allocation ratio to either anti-IL-8 or standard of care. Patients will be assessed daily while hospitalized. Discharged patients will be contacted by telephone on Day 29 and then monthly up to one-year to assess status. In addition to these specific assessment times, one interim analysis is planned at and the DSMC will actively monitor interim data to make recommendations about early signs of overwhelming efficacy and futility/study closure (see Section 13.4.)

With a sample size of 138 patients: N=92 patients randomized to the treatment arm and N=46 patients assigned to the standard of arm/control, the study will have 80% power to detect an increase in median time to improvement from 2 days (control) to 5 days (treatment arm) with one-sided alpha of 0.025. The sample size was estimated based on a hazard ratio (HR) of 0.40 assuming an exponential survival distribution with inflation to account for one interim look and 5% drop-out rate.

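### Time zero for the primary endpoint is undefined for the control arm and worded in two ways, so the two arms may be timed from different points

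*Combined protocol and SAP*

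**What the plan says.** The endpoint definition in Section 11.1.1, repeated in Sections 4.1 and 13.1, is "the time (days) required from the start of treatment to the improvement of clinical status (2 points) assessment from baseline". The primary objective, in the synopsis and Section 2, words it differently: "Measured from baseline to 2 point or greater improvement in 7-point ordinal scale".

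Baseline is not anchored in a way that applies to both arms. Footnote a of the Section 10 calendar says "The screening (pre-treatment) evaluation should be conducted within 1 day prior to dose of BMS-986253". Section 10.1 says "All of these evaluations should be conducted within 1 day of starting the protocol", and does not say what starts the protocol for a control patient.

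On the control arm, Section 4.1 says "Subjects randomized to the control arm will receive standard of care therapy as determined by their treating physician". No section defines a treatment start, Day 1 or time zero for these patients. No section sets the clock at randomisation or limits the time from randomisation to first dose.

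The start of treatment is also the anchor for 1-month mortality, time to improved oxygenation and the day-14 ordinal score (Sections 2, 11.2 and 13.2), and for the 28-day assessment (Sections 7.7 and 10.3).

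**The concern.** A time-to-event comparison needs an origin that exists in both arms and is fixed independently of the assigned treatment. Here the stated origin exists in one arm only. Following the text, an analyst times a treated patient from the infusion and must choose another anchor for each of the 46 controls: baseline, randomisation, or some date for standard of care. The trial is open label, so that choice could be made with the assignments known.

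If controls are timed from randomisation and treated patients from a later infusion, the days in between count for controls and are removed for treated patients. That makes the drug look faster without any drug effect. The scale is scored daily and the planning medians are 2 and 5 days, so a one-day offset is 20% to 50% of a median.

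**Working it through.** **1. The plan's own figure.** Inputs: HR 0.40, one-sided alpha 0.025, power 80%, 2:1 allocation (Sections 13.1 and 13.4). By Schoenfeld's formula:

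events = (1.960 + 0.842)² / [(2/3)(1/3)(ln 0.40)²] = 7.849 / (0.2222 × 0.8396) = 42.07.

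The plan states 41. At 41 events, power is Φ(0.9163 × √(41 × 2/9) − 1.960) = Φ(0.806) = 0.79, against the 80% stated. The figure is reproduced within rounding. The time origin does not enter it, so changing the origin leaves the events and N = 138 as they are.

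**2. The origin in each arm, as the text gives it.**

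| Source | Anti-IL-8 arm | Control arm |
|---|---|---|
| 4.1, 11.1.1, 13.1 (start of treatment) | first infusion | not defined |
| Synopsis, Section 2 (baseline) | score within 1 day before the dose (calendar) | calendar refers to a dose that controls do not receive |
| 10.1 (start of the protocol) | not defined | not defined |

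No row gives an origin that is defined in both arms.

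**3. What an offset would do.** The share of treated patients dosed on the day after randomisation is an assumption; the documents give no figure. Set-up: no drug effect; 92 v 46 patients; exponential times read in whole days; follow-up to day 28; log-rank test at one-sided 0.025; controls timed from randomisation. Treated patients dosed next day have one day removed, with a floor at day 0. There were 2,000 to 3,000 simulated trials per cell.

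Under no effect both arms share the control median. The synopsis gives that as 5 days and Section 13.1 as 2 days. At a 5-day median, 1 − 0.5^(28/5) = 0.979 of patients improve by day 28. So 138 patients give about 135 events, and 42 patients (28 v 14) give about 41. The second case approximates the planned final analysis.

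| Share dosed next day | 5-day median, 138 patients | 5-day median, about 41 events | 2-day median, 138 patients | 2-day median, about 41 events |
|---|---|---|---|---|
| 25% | 3.0-3.2% | 2.7% | 6.4-6.6% | 3.6% |
| 50% | 5.7-6.0% | 3.7% | 14-16% | 7.4% |
| 100% | 10-11% | 5-6% | 45% | 12-16% |

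Ranges come from separate runs. Monte Carlo error in the columns near 41 events is about 0.3 to 0.7 points. The scoring of patients who improve before the infusion also matters. If they are placed on day 1 and not day 0, the 100% row with 138 patients falls to about 7.6% (5-day median) and 28% (2-day median).

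**4. When nothing happens.** With one origin for both arms the simulated rate is about 2-3%. If treated patients who improve before the infusion are dropped, it is also 2.0-3.0%. That second result depends on the exponential model: given T > d, the remaining time T − d has the same distribution as T.

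**The case against.** The strongest reply is that baseline, as named in the objectives, can serve both arms. Randomisation is described as real-time, and screening must fall within a day of the dose. Screening, registration, randomisation and dosing may then share a calendar day, and an endpoint read in whole days shows no offset. This is a possible reading and the documents do not rule it out. It does not settle the matter, because three sections name a different origin and the calendar ties baseline to the dose.

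A reader might infer that the arms are in fact timed from different points. No section says so: the control origin is missing, and nothing states that it differs.

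A reader might also infer a built-in delay before dosing. The documents do not establish one:
- Section 6.1 says "Protocol therapy may not be initiated prior to receipt of this notification from the Central Registration Office". But Section 7.5 has the statistician send the assignment once eligibility is confirmed, and Section 6.1 places that confirmation within central registration. Registration therefore appears to come before randomisation and would delay both arms alike.
- The 120 minutes in Section 7.1 is the length of the infusion, which runs after treatment has started.
- The one-day window runs from screening to dose. It is not a randomisation-to-dose interval.

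The largest rates, 14% and 45%, are also tempting to quote. They need a 2-day control median, all 138 patients followed, and half or all of the treated patients dosed next day. The 2-day control median in Section 13.1 makes the treated arm the slower one, which looks like a reversal and is a separate matter.

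Finally, a patient who improves by two points before the infusion may never be dosed, and would then fall outside the populations in Sections 13.2 and 13.5.1 that require a dose. That could remove the inflation, but only under exponential times and only by dropping randomised patients from one arm.

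**Conclusion.** The point holds as a gap in definition. Time zero is undefined for controls, is worded in two ways, and as written gives treated patients an origin that controls cannot share. The arms may be timed differently; the documents do not show that they will be.

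Any resulting bias would favour anti-IL-8 if controls are timed from randomisation and treated patients from a later infusion. At the synopsis control median of 5 days it runs from negligible to about 10-11% with all patients followed, and to about 5-6% near 41 events, against 2.5% nominal. It is larger with a 2-day control median, and absent with a shared origin. These figures rest on an assumed share dosed next day and on exponential times.

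No effect was calculated for 1-month mortality, time to improved oxygenation or the day-14 score; they are included for consistency. This should be fixed, because the remedy is nearly free. It does not by itself invalidate the design.

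**What to change.** - Make randomisation time zero in both arms for the primary endpoint and, for consistency, for time to improved oxygenation, 1-month mortality and the day-14 score.
- Define baseline in both arms as the last ordinal score before randomisation.
- Count a two-point improvement at any time after randomisation as an event in both arms, including before the first dose in the anti-IL-8 arm. This works only if such patients stay in the primary analysis whether or not they are dosed, so the at-least-one-dose wording in 13.2 and 13.5.1 must not remove them.
- Record the date and time of randomisation for every patient. Section 7.5 says only that an assignment is sent.
- Align the synopsis and Sections 2, 4.1, 7.7, 10.3, 11.1.1, 11.2, 13.1 and 13.2. Changing the endpoint sections alone would leave the baseline wording in the objectives and the 28-day assessment on a different clock.

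The cost is wording and one recorded time. Treated patients' times become slightly longer. The 41 events and 138 patients stay as they are.
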